5.2 Secondary Objective(s)

A key secondary objective is to summarize the below outcome to confirm expected characteristics of the RP compared to SP:

1. Time to receipt of first injection of XR-NTX from day of admission for participants that receive first injection of XR-NTX while inpatient.

Additional key secondary objectives are to compare the below outcomes of RP versus SP for all enrolled participants (ITT population).

2. Craving for opioids measured by Visual Analog Scales (VAS).
3. Opioid withdrawal symptoms as measured by the Subjective Opioid Withdrawal Scale (SOWS) and the Clinical Opiate Withdrawal Scale (COWS).
4. Safety, as measured by overdose questionnaire, targeted safety events and serious adverse events.

Other secondary objectives are to compare the below outcomes of RP vs. SP for participants who receive the first injection while inpatient.

5. Retention in the trial to receive the second and the third XR-NTX injections.
6. Craving for opioids measured by Visual Analog Scales (VAS).
7. Opioid withdrawal symptoms following XR-NTX injection as measured by the Subjective Opioid Withdrawal Scale (SOWS)
8. Safety, as measured by overdose questionnaire, targeted safety events and serious adverse events.
9. Opioid abstinence, as measured by the Timeline Followback (TLFB) (self-report days using opioids) and proportion of opioid-positive urine tests.

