6.1.4.2 Phase 3 (Post-Induction Phase): Follow-Up Treatment

Following inpatient XR-NTX induction phase, participants will continue with the post-induction treatment for 8 weeks (post-induction Week 1 through Week 8; Days 1 – 55). Most participants will be treated on an outpatient basis during this phase, but some may be in extended residential or therapeutic community programs. Participants that receive first XR-NTX are expected to receive a second injection of XR-NTX towards the end of Week 4 and a third injection towards the end of Week 8 in combination with weekly Medical Management visits. The study will supply the three XR-NTX injections (initial and at Weeks 4 and 8). Study assessment visits occur weekly during this phase, with an End of Study (EOS) visit occurring at Week 8. For participants who request discontinuation of treatment, relapse, and/or become lost to follow up, a +14 day window is permissible to complete the EMT visit.

Patients who fail to initiate XR-NTX while inpatient will also be followed and evaluated at Week 4 and Week 8 to determine what treatment they are receiving (for example, whether they initiated XR-NTX after leaving the unit or if they initiated and remained on another medication (buprenorphine or methadone maintenance)) and whether or not they have relapsed to opioid use.

6.1.4.3 *Phase 4 (Referral Phase) Referral to continuing treatment*

During the last month of study, as part of standard clinical care, arrangements will be made by the clinical team for participants to either continue treatment at the same program or be referred to another program in the community for follow-up care, which should ideally include continuation of XR-NTX. The third XR-NTX injection will be administered as a part of the study in order to objectively assess the retention in treatment 8-weeks after the induction and to assure the continuation of treatment with XR-NTX during the post-study transition period. However, participants will not be followed with study assessments after third injection as at this point, they will be engaged with and followed in the community-based clinical care where they will be assessed medically following standard procedures.

6.1.4.4 *Management of participants who fail to initiate XR-NTX*

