16.3 Statistical Methods for Primary and Secondary Outcomes

16.3.1 Primary Outcome Analysis

As is standard for the analysis of stepped-wedge designs (Barker *et al.*, 2016) the primary outcome analysis for non-inferiority will be performed using a generalized linear mixed effects model with a logistic link, similar to the model used for the power calculations. The log odds of a participant receiving the first XR-NTX injection (yes/no) will be modeled as a function of which treatment they received (RP vs SP), which study month it is (to control for secular trends), and a random effect for site to control for nesting of participants within site. We will reject the null of inferiority of RP to

SP if the lower 95% confidence limit of the odds ratio of success [odds(RP)/odds(SP)] exceeds 0.67. Supplemental analyses related to the primary objective will test for a treatment*study month interaction, which, if significant, would indicate differential impact of treatment after a longer period of experience. Sensitivity analyses of the primary outcome may be performed to account for different correlation structures.

16.3.2 Secondary Outcome Analysis:

Secondary outcomes will include receiving 2nd and 3rd monthly injections of naltrexone, and opioid withdrawal symptoms and adverse events during and in the month after XR-NTX initiation. These outcomes will be modeled using similar mixed effects logistics regression methods as above. Note that the analysis of secondary outcomes before first XR-NTX injection will be performed using all enrolled participants using an intent-to-treat population (ITT) whereas the analyses of secondary outcomes after receipt of first XR-NTX injection will be performed for all enrolled participants as well as for a subset of the ITT population i.e., all enrolled participants who successfully received the scheduled XR-NTX injections (inducted population).

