3.1.5 Inducted Population

The inducted population consists of enrolled participants that receive the first XR-NTX while in the unit (i.e., all success for the primary outcome).

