8.4 Definition of the Secondary Outcome Measures

Key secondary analyses to be conducted by the DSC:

A key secondary objective is to summarize the below outcome to confirm expected characteristics of the RP compared to SP:

1. The time to receipt of first injection of XR-NTX as measured by the number of days from admission to first XR-NTX injection. This will be conducted on the successfully inducted population only. Day of admission is defined as Day 1 (E97ADMDT) as recorded on the ENRC or ENRD forms, and day of first XR-NTX injection (EOIINJDT) is captured on the End of Induction form (EOI). It will be calculated as Date of injection (EOI.EOIINJDT) – Date of admission (ENRC/ENRD.E97ADMDT) +1.

Additional key secondary objectives are to compare the below outcomes of RP versus SP for all enrolled participants (ITT population).

2. Craving for opioids measured by Visual Analog Scales (VAS) as captured daily on the self-reported inpatient opioid craving form (OCI) during induction phase. The OCI form collects intensity of craving both at time of assessment and within the last 24 hours prior to assessment. If either measurement is collected multiple times on the same assessment date, the average measurement will be used for analysis.
3. Opioid withdrawal symptoms as measured by the Subjective Opioid Withdrawal Scale (SOWS) and the Clinical Opiate Withdrawal Scale (COWS). SOWS is captured on the SBW form at baseline and daily during induction phase. COWS is captured on the COW

form starting with day of admission and daily during the induction phase leading to the first XR-NTX injection. Note that during induction, COWS may be measured multiple times per day while SOWS is expected to be assessed only once per day. If multiple SOWS measures are collected on the same assessment date, the average measurement will be used for analysis. If multiple COWS measures are collected on the same assessment, the peak measurement will be used.

4. Retention in the trial to receive at least one XR-NTX injection after the first injection as captured on the XR-NTX Administration (INN) form.
5. Safety, as measured by targeted safety events, overdoses, and serious adverse events related to study medication during the induction phase and during eight weeks of post-induction. Detail on safety outcome analysis is provided in Section 9.0.

Other secondary analyses to be conducted by LN:

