Other secondary objectives to be analyzed by the LN are to compare the below outcomes of RP vs. SP for participants who receive the first injection while on the unit (Inducted Population):

- Opioid abstinence, as measured weekly by the Timeline Followback (TLFB) (self-report days using opioids) during the eight weeks of post-induction and proportion of opioid-positive urine tests as captured on the Urine Drug Screen (UDS) form at post-induction 4 week and 8 week visits.
- In addition, craving for opioids, opioid withdrawal symptoms, and safety events will be assessed in the inducted population similar to the key secondary outcomes.

Table 5: Secondary Clinical Outcomes, Outcome Measures and Hypotheses		
Outcome	Outcome Measure	Hypothesis
Time from admission to first XR-NTX injection	Days to first XR-NTX injection	Participants in the RP will receive their first injection significantly faster than those in the SP. Significance/Rationale: The RP decreases the time to the first injection (which has a potential to decrease costs and staff burden).
Opioid craving (VAS) over time	Mean for opioid craving measured by VAS daily during days leading to the first XR-NTX injection, and during post-induction Weeks 1-8	Participants in RP and SP will have comparable intensity of craving during 1) the inpatient treatment period, and 2) during the first week after the first XR-NTX injection. Significance/Rationale: Earlier trial showed comparable craving severity in both procedures (Sullivan et al. , 2017).
Opioid withdrawal (SOWS and COWS) over time	Mean for opioid withdrawal measured by SOWS and COWS score, daily (starting with day of admission) during days leading to the first XR-NTX injection and during post-induction Weeks 1-8	Participants in RP and SP will have comparable severity of opioid withdrawal during: 1) the inpatient treatment period, and 2) during the first four weeks after the first XR-NTX injection. Significance/Rationale: Earlier trial showed comparable withdrawal severity in both procedures (Sullivan et al. , 2017).

Table 5: Secondary Clinical Outcomes, Outcome Measures and Hypotheses

Outcome	Outcome Measure	Hypothesis

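### Post-induction opioid use, craving and SOWS are compared only among induction successes, although Protocol 16.3.2 also calls for all enrolled participants; reconcile the sections and add an ITT comparison

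*SAP*

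**What the plan says.** The documents give two answers on who is compared after induction.

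The narrower answer is in the objectives. Protocol 5.2: "Other secondary objectives are to compare the below outcomes of RP vs. SP for participants who receive the first injection while inpatient". Retention, craving, SOWS, safety and opioid abstinence follow under that sentence, and SAP 2.1.2 repeats the list. SAP 8.4 implements it: opioid abstinence (Timeline Followback and urine screens) is there to "compare the below outcomes of RP vs. SP for participants who receive the first injection while on the unit (Inducted Population", and "craving for opioids, opioid withdrawal symptoms, and safety events will be assessed in the inducted population similar to the key secondary outcomes". SAP 3.1.5 defines the group: "The inducted population consists of enrolled participants that receive the first XR-NTX while in the unit (i.e., all success for the primary outcome".

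The wider answer is in the protocol's analysis section. Protocol 16.3.2: "analyses of secondary outcomes after receipt of first XR-NTX injection will be performed for all enrolled participants as well as for a subset" of inducted participants.

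The SAP does analyse craving and withdrawal in the ITT population, but only up to the end of induction. Craving, for instance, is "captured daily on the self-reported inpatient opioid craving form (OCI) during induction phase". Induction failures stay in the study and are seen at Weeks 4 and 8. Protocol 6.1.4.2 gives the purpose as learning what treatment they are receiving and "whether or not they have relapsed to opioid use".

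**The concern.** The inducted set is formed after assignment, and membership is the primary outcome itself. If the two procedures induct different kinds of patient, the inducted groups are not comparable, and randomising sites does not repair that. The plan gives reason to expect such differences. Protocol 16.8 and SAP 8.3 name severity, route of use, type of opioid and comorbidity as predictors of induction, and Protocol 4.1.2 reports more induction failure among heroin users in an earlier outpatient study.

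If RP inducts more patients, some of the extra ones may carry a poorer prognosis and make RP look worse on opioid use. If RP inducts fewer, which Protocol 4.1.2 allows for by noting that stronger withdrawal could lower retention, the distortion can run the other way. At stake is whether the trial can say anything about opioid use in the groups its design assigned. The relapse information collected on induction failures would otherwise enter no planned comparison of opioid use.

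**Working it through.** **Is there an all-enrolled comparison elsewhere?** In SAP 8.6, item 5 covers alcohol and other drugs, and its examples name no opioid. Items 7 to 9 cover MOUD use and XR-NTX receipt. Item 4 covers PHQ-9 and GAD-7. None compares post-induction opioid use, VAS craving or SOWS by procedure in everyone enrolled. SAP Table 1 points the other secondary outcomes to Section 8.5, which gives no model for opioid use. The revision history in SAP 16.0 gives no reason for choosing the narrower population.

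**Are data available?** SAP 2.2.2 schedules Timeline Followback, the outpatient craving form and SOWS at post-induction visits, and failures attend Weeks 4 and 8. Protocol 12.2.5 has the Timeline Followback cover every day since the previous one, so two visits can span the eight weeks.

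**Planning rates.** SAP 12.0 assumes success of 0.55 in SP and 0.70 in RP. Its odds ratios reproduce: (0.45/0.55)/(0.55/0.45) = 0.669 for the margin and (0.70/0.30)/(0.55/0.45) = 1.909 for the alternative, against the stated 0.67 and 1.91. This point disputes no stated figure.

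**Size of the selection.** Protocol 8.0 plans about 225 participants per procedure.
- Inducted under SP: 225 x 0.55 = 124. Inducted under RP: 225 x 0.70 = 158.
- If RP inducts everyone SP would (assumption), the share of the RP inducted set that SP would not have inducted is (0.70 - 0.55)/0.70 = 0.214.

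**Effect on the comparison.** Let *a* be opioid use in those inducted under either procedure, *m1* use in the RP-only inductees when inducted, and *m0* use in the same people when not inducted. Assume no procedure effect among those inducted either way, and equal use across procedures in those inducted under neither. Then, RP minus SP:
- inducted only: 0.15 x (*m1* - *a*)/0.70
- all enrolled: 0.15 x (*m1* - *m0*)

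The documents give no opioid-use rates. With assumed *a* = 20% and 70% use in anyone not inducted:

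| Assumed *m1* | Inducted only (points) | All enrolled (points) |
|---|---|---|
| 10% | -2.1 | -9.0 |
| 20% | 0.0 | -7.5 |
| 30% | +2.1 | -6.0 |
| 40% | +4.3 | -4.5 |
| 60% | +8.6 | -1.5 |

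In full at 40%, inducted only: SP 20.0%, RP (0.55 x 0.20 + 0.15 x 0.40)/0.70 = 24.3%. All enrolled: SP 0.55 x 0.20 + 0.45 x 0.70 = 42.5%, RP 0.55 x 0.20 + 0.15 x 0.40 + 0.30 x 0.70 = 38.0%.

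Other assumed rates, still with *m1* = 40%: *a* = 10% and 80% if not inducted gives +6.4 and -6.0; *a* = 30% and 60% gives +2.1 and -3.0.

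If RP inducted 45% against 55% in SP, with *a* = 20%, 40% use in the SP-only inductees when inducted and 70% in anyone not inducted, the inducted-only difference is 0.20 - (0.45 x 0.20 + 0.10 x 0.40)/0.55 = -3.6 points. The all-enrolled difference is 0.10 x (0.70 - 0.40) = +3.0 points.

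With RP inducting more, the signs oppose when *m1* lies between *a* and *m0*. At *m1* = 20% the inducted-only difference is nil, and at 10% both comparisons favour RP.

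**The case against.** A reader might infer that the SAP simply dropped a promised analysis. The documents do not support that. Protocol 5.2 restricts these objectives to inducted participants, and the SAP follows it closely. Protocol 16.3.2 also does not name opioid use or craving: it lists second and third injections, withdrawal symptoms and adverse events, and reaches the other outcomes only through its general sentence on analyses after the first injection. The protocol disagrees with itself, and the SAP took one side.

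A reader might also infer that the hypothesis of comparable opioid use goes untested. As written in Protocol Table 3 and SAP Table 5, that outcome concerns use while on study medication and is justified by opioid blockade. The inducted population is a natural set for that question. An ITT comparison answers a different one.

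Nor are failures ignored. Safety events and overdoses are summarised by procedure in all consented participants, and several exploratory items include or concern failures. The disputed comparisons are lower-tier analyses, and SAP 11.0 promises cautious interpretation of secondary results without multiplicity control.

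The assumed opioid-use rates are illustrative. The plan expects use on medication to be minimal and similar between procedures. If the extra RP inductees behaved like the rest, the inducted-only difference would be zero.

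All of this stands, and it limits the point. It does not remove the conflict between Protocol 5.2 and 16.3.2, the conditioning on the primary outcome, or the missing all-enrolled comparison of opioid use.

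**Conclusion.** The point holds as a conflict to reconcile and an inexpensive analysis to add. The SAP silently adopts the narrower population, and its between-procedure comparison of post-induction opioid use, craving and SOWS then conditions on the primary outcome.

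At the planned rates about 21% of the RP inducted set would be patients SP would not have inducted, if RP inducts everyone SP would. The bias can go either way. It is tempting to conclude that the inducted-only result will reverse the all-enrolled one, but the documents do not show this. Reversal depends on opioid-use rates they do not give, on that monotone-induction assumption and on no procedure effect among those inducted either way. It occurs over part of the assumed range and not over the rest. The primary analysis is unaffected.

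**What to change.** Reconcile Protocol 5.2, Protocol 16.3.2 and SAP 8.4 on the population for outcomes after the first injection. In the same edit align the definition of the inducted subset: Protocol 16.3.2 refers to receipt of the scheduled injections, SAP 3.1.5 to the first injection on the unit.

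Add to SAP 8.4 and 8.5 an ITT comparison of RP and SP on:
- Timeline Followback opioid use over post-induction Weeks 1-4 and 5-8;
- craving and SOWS at the common Week 4 and Week 8 visits.

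Put procedure, step and site in the model. State the time origin: under SAP 3.2.2, Day 1 is the day after the injection or the day after failure, so it falls at different times since admission. Specify a missing-data sensitivity analysis, since SAP 8.7 addresses only the primary outcome.

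Keep the inducted-population comparisons, as Protocol 16.3.2 provides for both. State that they condition on a post-assignment outcome and answer an on-medication question.

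The cost is SAP and protocol wording and a few more models on data already scheduled. The downside is data quality. Failures have two visits rather than six, so they recall about four weeks where inducted participants mostly recall one or two, and more data will be missing. Few urine screens will exist for failures because Protocol Table 7 ties screens to injections, so the ITT comparison of opioid use rests on self-report.

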7.2 Secondary Outcome Measure(s)

7.2.1 Table 3: Secondary Clinical Outcomes, Outcome Measures and Hypotheses

Outcome	Outcome Measure	Hypothesis
Time from admission to first XR-NTX injection	Days to first XR-NTX injection	Participants in the RP will receive their first injection significantly faster than those in the SP. Significance/Rationale: The RP decreases the time to the first injection (which has a potential to decrease costs and staff burden).
Opioid Craving (VAS) over time	Mean for opioid craving measured by VAS daily during days leading to the first XR-NTX injection, and during post-induction Weeks 1-8	Participants in RP and SP will have comparable intensity of craving during 1) the inpatient treatment period, and 2) during the first week after the first XR-NTX injection. Significance/Rationale: Earlier trial showed comparable craving severity in both procedures (Sullivan et al. , 2017).
Opioid withdrawal (SOWS and COWS) over time	Mean for opioid withdrawal measured by SOWS and COWS score, daily (starting with day of admission) during days leading to the first XR-NTX injection and during post-induction Weeks 1-8	Participants in RP and SP will have comparable severity of opioid withdrawal during: 1) the inpatient treatment period, and 2) during the first four weeks after the first XR-NTX injection. Significance/Rationale: Earlier trial showed comparable withdrawal severity in both procedures (Sullivan et al. , 2017).
Receive second and third injections (binary: did or did not receive second and third dose of XR-NTX)	Proportion of participants that receive second and third injection of XR-NTX (at 4 weeks and 8 weeks, from first injection)	Participants in RP and SP will have comparable rates of treatment retention. Significance/Rationale: Because there is no difference in tolerability of the first and second XR-NTX injections in both study arms, we do not expect differential treatment dropout.
Targeted safety events, overdoses and SAEs, related to study medications	Frequency of targeted safety events, overdose episodes and SAEs by relationship to study medication during the induction period and during eight weeks of post-induction	RP and SP will produce equivalent rates of targeted safety events and SAEs during the induction and during the first eight weeks of treatment with XR-NTX. Significance/Rationale: Careful documentation of SAEs, targeted safety events, and overdose

Outcome	Outcome Measure	Hypothesis

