  random intercept / subject=patid type=ar(1);  
run;
```

where:

- trt - is the variable that defines the induction procedure (RP or SP)
- outcome - is the presence of moderate to severe daily COW score (Yes=1 or No=0)
- step - is 1 through 5
- site - is the site code for the 6 sites.
- day- days since admission to the unit
- patid- participant ID

SAS code example that may be used to analyze continuous SOWS and VAS outcomes:

```
proc mixed data = secondout;  
  class patid site day_cat trt(ref='SP') step (ref='1');  
  model outcome = trt site day step/ solution cl;  
  random intercept / subject = patid;  
  repeated day_cat/ type = AR(1) subject = patid;  
  estimate "trt effect" trt 1 -1;  
run;
```

where:

- trt - is the variable that defines the induction procedure (RP or SP)
- outcome - is either mean SOWS or mean VAS score
- step - is 1 through 5
- site - is the site code for the 6 sites
- day - days since admission to the unit (continuous)
- day_cat- days since admission to the unit (categorical) as required by the repeated statement in the model
- patid- participant ID

Retention in the trial to receive at least one XR-NTX injection after the first inpatient injection as captured on the XR-NTX Administration (INN) form will be analyzed similarly to the primary outcome using a mixed-effects model with logit-link function.

Frequency of targeted safety events, overdose episodes and SAEs by relationship to study medication will be reported. Safety data analysis is provided in detail in Section 9.0.

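### The post-injection window for craving and withdrawal differs between hypothesis, outcome measure and analysis text, and no contrast matching the hypotheses is prespecified

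*SAP*

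**What the plan says.** Protocol Table 3 (7.2.1) and SAP Table 5 (8.4) carry the same rows.

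- **Craving.** The outcome measure is "Mean for opioid craving measured by VAS daily during days leading to the first XR-NTX injection, and during post-induction Weeks 1-8". The post-injection part of the hypothesis is "2) during the first week after the first XR-NTX injection".
- **Withdrawal.** SOWS and COWS are to be averaged "daily (starting with day of admission) during days leading to the first XR-NTX injection and during post-induction Weeks 1-8". The post-injection part of the hypothesis is "2) during the first four weeks after the first XR-NTX injection".
- **Protocol 16.3.2** gives yet another description for withdrawal: "opioid withdrawal symptoms and adverse events during and in the month after XR-NTX initiation". That fits the four-week hypothesis and not Weeks 1-8.

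SAP 8.4 defines the key secondary craving and withdrawal outcomes for the induction phase. It leaves the inducted population to the lead node, to be handled in the same manner as the key secondary outcomes, and states no window. SAP 8.5 says the longitudinal scores may be analysed with mixed models. Its example for SOWS and VAS is "model outcome = trt site day step/ solution cl", where day means days since admission. SAP Tables 47 and 48, which would hold the model results, are titled for the induction phase.

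SAP 2.2.2 schedules post-induction assessments at Weeks 1, 2, 3, 4, 6 and 8 and lists no COWS there. Protocol Table 7 has none either. The post-injection withdrawal objective (Protocol 5.2, SAP 2.1.2) names SOWS only.

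**The concern.** An analyst following the tables would estimate a Weeks 1-8 quantity, while the stated hypotheses concern one week and four weeks. The example model has no procedure-by-time term, so it returns a single procedure effect across whatever visits enter it.

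Its clock also does not line the arms up after the injection. Protocol 16.1.2 puts the end of induction at about Day 6 in RP and Day 13 in SP, so the same visit after injection falls about 13 - 6 = 7 days apart on the admission scale.

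The timing matters because Protocol 4.1.2 names more severe precipitated withdrawal, during titration or after XR-NTX, as a risk of the rapid method. An excess of that kind could be early and short. Both hypotheses predict comparable arms and neither document gives a margin, so diluting an early difference moves the estimate towards the predicted answer. In an open-label trial, leaving the window open also leaves the choice of contrast to be made after data have been seen.

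**Working it through.** The documents give no power, SD or margin for these outcomes, so there is no stated figure to reproduce.

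**Inputs from the documents**
- Six post-induction visits for inducted participants (SAP 2.2.2). One falls in the craving window and four in the withdrawal window.
- Design matrix with 15 RP and 15 SP cells of 15 participants: 225 per procedure, agreeing with Protocol 8.0.
- Assumed success 0.55 (SP) and 0.70 (RP). Expected inducted: 225 × 0.55 = 123.75 and 225 × 0.70 = 157.5, that is 8.25 per SP cell and 10.5 per RP cell.
- Two-sided 5% tests for secondary outcomes (SAP 11.0).

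**Assumptions not in the documents**
- VAS SD 30 (also 20), within-person correlation 0.5, and a 10-point RP excess at Week 1 only.
- No missed visits.

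**Step 1: dilution in a single pooled contrast**

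Equal weights:
- Week 1 only: 1/6 = 17%.
- Weeks 1-4: 4/6 = 67%.

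Under AR(1) with parameter φ, treating the six visits as equally spaced, the generalised least squares weight is 1/(6 - 4φ) for the first and last visit and (1 - φ)/(6 - 4φ) for each of the others. A random intercept leaves these weights unchanged.

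| φ | Week 1 share | Weeks 1-4 share |
|---|---|---|
| 0 | 0.167 | 0.667 |
| 0.3 | 1/4.8 = 0.208 | 3.1/4.8 = 0.646 |
| 0.5 | 1/4.0 = 0.250 | 2.5/4.0 = 0.625 |
| 0.7 | 1/3.2 = 0.313 | 1.9/3.2 = 0.594 |

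**Step 2: standard errors before adjustment (SD 30)**
- Week 1: 30 × √(1/123.75 + 1/157.5) = 3.60.
- Six-visit mean: 3.60 × √((1 + 5 × 0.5)/6) = 2.75.

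**Step 3: adjustment for site and step, as in the SAP code**

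Regress the RP indicator on site and step over the 30 cells, weighted by expected inducted participants. The residual sum of squares is 21.7. Without site and step it is 69.3. The variance inflation is 69.3/21.7 = 3.19, so each SE is multiplied by √3.19 = 1.79.
- SD 30: Week 1 SE 6.44, six-visit SE 4.92.
- SD 20: Week 1 SE 4.29, six-visit SE 3.28.

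**Step 4: power = Φ(effect/SE - 1.96) + Φ(-effect/SE - 1.96)**

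The effect is 10 at Week 1 and 10/6 = 1.67 in the six-visit mean.

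| | Week 1 visit | Six-visit mean |
|---|---|---|
| SD 30, site and step adjusted | 34% | 6% |
| SD 20, site and step adjusted | 64% | 8% |
| SD 30, unadjusted | 79% | 9% |
| SD 20, unadjusted | 99% | 15% |

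The adjusted rows are the relevant ones, because the SAP code fits site and step.

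**The case against.** A reader might infer that the plan commits to one pooled Weeks 1-8 mean, and that an early RP excess would therefore be averaged away and the arms declared comparable. The documents do not support that.

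- Both rows are headed as outcomes over time, and scores are taken at each visit. A mean during Weeks 1-8 can be read as a mean at each visit.
- The key secondary analysis that is to be imitated begins with summaries for each day. The mixed model is something that may be used, and no post-induction version of it is written.
- For withdrawal, an excess lasting the hypothesised four weeks would be reduced and not erased. Protocol 16.3.2 already points to the month after initiation.
- Acute precipitated withdrawal has other routes to detection. It is a targeted safety event, reported by phase with Fisher's exact test (SAP 3.2.6, 10.1, Table 52). SAP Tables 44-46 tabulate withdrawal and craving on the injection day, before and after the injection.
- Neither document says that non-significance will be read as comparability.
- The unadjusted 79% against 9% overstates what a Week 1 contrast can deliver. At SD 30 with site and step in the model, it would miss a 10-point excess about two times in three.

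All of this stands. It limits the claim to an inconsistent and unspecified window. It does not remove the mismatch within the rows, which no other passage resolves for craving, or the absence of a contrast on time since injection.

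**Conclusion.** The inconsistency holds for both outcomes: one week (craving) and four weeks (withdrawal) in the hypotheses, about a month in Protocol 16.3.2 for withdrawal, and Weeks 1-8 in the outcome measures. COWS is also named for a period in which none is scheduled.

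The harm is conditional. If the optional single-term model is applied to the six visits, a craving excess confined to Week 1 keeps about 17% of its size (21-31% under AR(1) with parameter 0.3-0.7), and a withdrawal excess over Weeks 1-4 keeps about 59-67%. The power figures of 34% against 6% (SD 30) and 64% against 8% (SD 20) rest on an assumed SD, correlation and effect. They also rest on the planned enrolment and success rates, and on no missed visits.

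This should be corrected, but it does not threaten the trial's main conclusion. SAP 11.0 describes the key secondary outcomes as not confirmatory, and the primary analysis does not use these scores.

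**What to change.** 1. In Protocol Table 3 and SAP Table 5, set the post-injection outcomes to VAS at the Week 1 visit and SOWS over Weeks 1-4. Keep Weeks 1-8 as supplementary.
2. In SAP 8.5, add a post-induction model for the inducted population. Use visit since injection as a class variable, a procedure-by-visit term, and site and step as now. Report the Week 1 VAS contrast and the Weeks 1-4 SOWS contrast with confidence intervals.
3. State that a non-significant difference will not be taken as evidence of comparability.
4. Delete COWS from the post-induction outcome measure.

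The cost is table wording, one interaction term and the matching output shells. No new data are needed. The drawback is precision: the Week 1 craving contrast rests on one visit, and its SE is about 6.4 points at SD 30 (4.3 at SD 20) once site and step are adjusted for, so a wide interval should be expected and reported as such.
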